NCT03232801

Title: A Mindfulness-based Intervention for Older Women with Low Sexual Desire

Date: August 1, 2022

Statistical analysis:

We assessed satisfaction and likelihood of recommending the group to another woman with low libido at 7 weeks (primary outcome). We assessed sexual function [Female Sexual Function Index (FSFI)] and sexual distress [Female Sexual Distress Scale-Revised (FSDS-R)] at 12 weeks (exploratory outcomes). We used chi squared statistics to examine differences in primary outcomes between groups. We constructed linear regression models to compare changes in FSFI and FSDS-R from baseline to 12 weeks for each group.

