Study protocol

NCT03232801

Title: A Mindfulness-Based Intervention for Older Women with Low Sexual Desire

Version date: August 1, 2022

Study Rationale

Sex is a fundamental component of overall well-being for many adults. Individuals who maintain a healthy sex life with aging live longer and have high quality of life. However, sexual function problems are common, particularly among midlife women; 39% of this population struggles with low sexual desire. This can affect not only a woman's sex life, but also negatively impact on psychosocial functioning and relationships.

Despite success in developing treatment for men, there has been a lack of treatment options for women. An increasingly accepted model of female sexual response emphasizes both physiologic and psychologic aspects of female sexual function. Pharmacologic treatments that only target physiologic response will only help a subset of women. In contrast, behavioral interventions have the potential to target both physiologic and psychological aspects of female sexual function. Using this rationale, this study will look at the use of a mindfulness study to improve sexual function in midlife women. Female sexual dysfunction is associated with sexually-related anxiety, autonomic nervous system imbalance, negative body image, discursive negative thoughts that distract during sex, and poor sleep.

Using this rationale, this study will look at the use of a mindfulness study to improve sexual function in midlife women. Mindfulness, a concept that emphasizes in-the-moment focus and non-judgmental bodily awareness, can target all these aspects of sexual dysfunction simultaneously by decreasing anxiety, improving autonomic imbalance, enhancing body image, reducing distracting thoughts, and improving sleep.

Treating sexual dysfunction will result in improvements in women's sexuality and can have the opportunity to go beyond sex to improve relationships and overall quality of life in aging adults. At least 85% of women in the intervention group will indicate somewhat or very satisfied on a measure of the intervention satisfaction.

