Screen failures are defined as participants who consent to participate in this study but are not subsequently assigned to the study intervention or entered in the study. Individuals who do not meet the criteria for participation in this trial (screen failure) because of meeting one or more exclusion criteria are thanked for their time and given the opportunity to ask any questions. Examples of exclusions are those that have severe pain with vaginal penetration, more than 7 drinks in a week, or those who do not have a partner with whom they would like to be sexually active.

Strategies for Recruitment and Retention

Each group (control and experimental) will have roughly 12-15 people in order to keep the group size comfortable. If participant number is fewer than 12 people per group, the sessions can still be held. As long as participants are willing to join and participate, the sessions can still go on. We are limiting our recruitment only to women who are 45 years and older. Due to the nature of this study, participants must be proficient in English.

Women will be recruited via: (a) flyers placed at local internal medicine, gynecology, and sex therapy clinics; (b) advertisements in University of Pittsburgh and UPMC staff e-mail newsletters, in newspapers, and on buses; (c) presentations to UPMC providers that care for midlife women; (d) social media advertisements such as Facebook; (e) the CTSI Research Participant Registry; and (f) Pitt + Me. The advertisement used for Facebook will only be posted on the personal pages of study staff, and we will not encourage others to "Share" the posting.

We will obtain verbal consent to perform telephone screening procedures, which involve minimal risk to the potential participant using the screening survey on RedCap. After telephone screening procedures, women who are eligible can be mailed or emailed detailed information on the study, if they are interested.

For participants, the study will initially be described over the phone. Participants will have the opportunity to ask questions about the study at this time. The Research Assistant will review the consent form and any risks associated with the study. Participants will be given the opportunity to verbally consent at that time or to read over more information that will be sent by email or snail mail. This will take about 20 minutes.

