If uncomfortable with the study requirements, the participant may choose not to enroll in the study at this time. If the person decides to participate, they will be asked to complete a verbal consent over the phone. All documents specifically state that participation in the study is voluntary and the decision NOT to participate in the study will not have negative consequences for the participant.

In order to increase retention and keep participants interested, women will receive \$25 for completing each of the three assessments. An extra \$25 will be given for completing all three assessments, for a total of \$100 per participant. If interested, participants can complete an optional interview about the study at the completion of the sessions for a bonus of \$20.

STUDY INTERVENTION OR EXPERIMENTAL MANIPULATION DESCRIPTION

Women will be randomized into two separate groups. The active control group will attend six, two-hour sessions over six weeks in groups of approximately 12-15 women. The content of these sessions will focus on general health and aging (e.g., cardiovascular health, osteoporosis) and will include only limited information on sexual health. The use of an active control allows the study to control for group support and attention. It will also allow the study to explore women's willingness to be randomized.

Intervention will be given in the form of in person mindfulness training, including self-observation, meditation techniques, gentle yoga, and attention to breath. Additional content will include general sex education, sensate focus, and couples therapy, such as information on potential etiologies of sexual function and sexual response, bodily exploration exercises, and communication training.

Both women in the control group and the experimental group will be lead by the PI and a trained expert in mindfulness-based stress reduction. Women in both groups have the opportunity to complete an optional phone interview with a RA at the completion of the sessions on their experience.

Administration

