Following the screening, participants will be sent a survey link to complete all the baseline activities. Once the intervention starts, participants will attend a weekly virtual session with other members of their group (control vs variable). These sessions will last for six weeks at approximately two hours each. In these sessions, they have the possibility of interacting with members of their group and with the leaders of each group. However, group participation is up to the participant; they are able to share as little or as much as they feel comfortable. Following the completion of the sessions, a survey will be sent to participant. These surveys will be identical to the baseline surveys, excluding the surveys on Demographics, Relationship Variables, Frequency of Sexual Activities, and Medical Variables. There will also be an Acceptability of Intervention survey sent out at the finish of the sessions. Participants will have one week to fill out and return the surveys, which will be tracked through RedCap.

At the 12 week mark, a final set of surveys will be sent out, identical to the baseline surveys, excluding the surveys on Demographics, Relationship Variables, Frequency of Sexual Activities, and Medical Variables. Participants will have one week to fill out and return the surveys, which will be tracked through RedCap.

Interventionist Training and Tracking

To ensure the completion of all surveys, in the week the survey is disseminated, progress will be monitored using RedCap. All surveys need to be returned within the week they are sent out so if progress is not being made by a participant, the RA will reach out up to three different times to send reminders and check in. The three contact points can be made via different methods, including through email and phone call.

Discontinuation/Withdrawal

An investigator may discontinue a participant from the study for the following reasons:

- Significant study intervention non-compliance, unless varying compliance is an aspect of the study objectives
- Lost-to-follow up
- Any event or medical condition or situation occurs such that continued collection of follow-up study data would not be in the best interest of the participant or might require an additional treatment that would confound the interpretation of the study
- The participant meets an exclusion criterion (either newly developed or not previously recognized) that precludes further study participation

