Participants are allowed to withdraw at any time for any reason. Data up until the point a participant discontinued the study will be included in the study. Participants will not continue with surveys when participation is discontinued.

If a participant misses more than 2 meetings, they are withdrawn from the study. They are still eligible for payment if they completed the first survey. If there are further six-week sessions, a participant can move to a later session that may fit their schedule.

Loss to Follow-Up

The following actions must be taken if a participant fails to return their surveys in the correct amount of time:

- The site will attempt to contact the participant, remind them of the studies they have left to complete, counsel the participant on the importance of maintaining the assigned visit schedule, and ascertain if the participant wishes to and/or should continue in the study
- Before a participant is deemed lost to follow-up, the investigator or designee will make every effort to regain contact with the participant. The investigator or designee will make up to 3 different attempts at contact with the participant. These attempts will include reaching out via phone or email.
- Should the participant continue to be unreachable, they will be considered to have withdrawn from the study with a primary reason of lost to follow-up.

Weekly Meetings

Meetings for each group will be held on separate days. Following recruitment, a survey will be sent out to the participants to each group. Any survey system can be used to generate the surveys to gauge interest in the best day and time for the group (Qualtrics was used). Make sure that each group has a separate survey (i.e. an availability survey for both the mindfulness (experimental) and educational (control) group).

Give the groups around one week to answer, sending out 1-2 reminders. Once a day and time is decided on, meetings can begin. An email can be sent to participants with the upcoming dates and the Zoom link. To ensure participants remember the meeting, an email should be sent every week, 12-24 hours before the meeting with the zoom link.

Meetings are held every week for six weeks total. Meeting length is variable, but participants should prepare for a two-hour meeting.

At each meeting, a research assistant should take attendance and keep track of who is coming to the meetings. This is important to record to ensure participants are making it to at least 4 meetings.

Payment

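### Does comparing graded satisfaction answers by chi-squared, with no stated levels or cut-point, cost the trial power that an ordered test would keep?

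*SAP*

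**What the plan says.** The SAP is a single paragraph under Statistical analysis. It names the primary outcomes and their timing: "We assessed satisfaction and likelihood of recommending the group to another woman with low libido at 7 weeks (primary outcome"). The between-arm analysis is one sentence: "We used chi squared statistics to examine differences in primary outcomes between groups". Table dimensions, response levels, a cut-point and a trend or rank version are not mentioned.

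The Protocol adds two pieces. Study Rationale sets a benchmark: "At least 85% of women in the intervention group will indicate somewhat or very satisfied on a measure of the intervention satisfaction". This shows that satisfaction is graded and groups its top two grades, but for the intervention arm only and without reference to the between-arm test. Administration names the instrument ("There will also be an Acceptability of Intervention survey sent out at the finish of the sessions") without its items or response options. That likelihood of recommending is also graded is an inference from its name.

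Numbers per arm are not firmly stated. Strategies for Recruitment and Retention says "Each group (control and experimental) will have roughly 12-15 people in order to keep the group size comfortable", and the intervention description repeats the figure as a session size ("in groups of approximately 12-15 women"). Discontinuation/Withdrawal allows for later cohorts: "If there are further six-week sessions, a participant can move to a later session that may fit their schedule". No total sample size, alpha, planned power or expected rates are given.

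**The concern.** An ordinary chi-squared test on a table with several ordered levels ignores the order. It spreads a one-directional shift over several degrees of freedom, where a trend or rank test spends one. If satisfaction or willingness to recommend moved up across the whole scale, the unordered test would be more likely to miss it on the same answers. This is the only stated between-arm comparison of the primary outcomes, and session groups are small, so the choice of test could decide the result. A second worry is that, with neither levels nor cut-point written down, the table could be laid out after the answers have been seen.

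**Working it through.** The plan states no power or sample-size figure, so there is none to reproduce. The check asks what each reading of the SAP sentence would cost.

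**Inputs.** From the Protocol: the top two grades of satisfaction as a grouping, 85% as a rate for the intervention arm, and 12-15 women per session group. Assumed, because the documents do not give them: four levels, two-sided 5%, 1:1 allocation, 60% in the top two grades in the control arm, and 15, 30 or 45 women per arm (the larger two standing for pooled cohorts).

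**Step 1: cost of degrees of freedom alone.** The noncentrality that gives 80% power on 1 df is (1.960 + 0.842)² = 7.85. The same value gives 71% power on 2 df, 64% on 3 df and 60% on 4 df (three, four and five levels). The method point is therefore correct if all levels are tested unordered and the ordered test captures the whole shift.

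**Step 2: the two-by-two reading.** For 85% against 60%, power is Φ{[0.25√n − 1.96√(2 × 0.725 × 0.275)] / √(0.85 × 0.15 + 0.60 × 0.40)}, where 0.725 is the mean of the two rates.

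- n = 15: (0.968 − 1.238) / 0.606 = −0.44, power 33%.
- n = 30: (1.369 − 1.238) / 0.606 = 0.22, power 59%.

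Simulation gives 35% and 60%. This test addresses the grouped proportion directly.

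**Step 3: the three tests under four patterns.** The reference arm is 5/10/35/50% from lowest to highest grade. The tests are Pearson on all levels, Pearson on the top two grades against the rest, and Wilcoxon with tie and continuity corrections. At least 60,000 tables were simulated per setting.

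| Pattern in the comparison arm | Odds ratios at the three cuts | Power at 15 per arm: all levels / 2×2 / Wilcoxon | At 30 per arm |
|---|---|---|---|
| Broad shift, 15/25/40/20% | 3.4, 3.8, 4.0 | 31 / 35 / 48% | 63 / 60 / 79% |
| Concentrated at the grouping, 13/27/25/35% | 2.8, 3.8, 1.9 | 19 / 35 / 23% | 41 / 60 / 43% |
| Between the top two grades only, 5/10/65/20% | 1, 1, 4.0 | 31 / 4 / 26% | 58 / 5 / 47% |
| Non-monotone, 20/5/20/55% | 4.8, 1.9, 0.8 | 16 / 10 / 5% | 39 / 16 / 5-6% |

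Each odds ratio compares the odds of answering above the cut. At the middle cut of the first row, for example, (0.85/0.15) / (0.60/0.40) = 3.8.

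The loss in the first row is real. With exact permutation p-values for both tests the figures at 15 per arm are 34% and 47%, so the gap comes mainly from ignoring order and not from a conservative approximation. But Wilcoxon is best only in that row.

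**Step 4: how quickly the ranking turns.** Hold the top-two rates at 85% and 60% and the comparison arm's lower grades at 15/25%, then raise its share in the top grade from 20%. Wilcoxon beats the 2×2 test only up to a share of about 27% at 15 per arm and 28-29% at 30. The odds ratio at the top cut is then about 2.5-2.7, still a clear upward shift.

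**Step 5: validity.** With 5/10/35/50% in both arms at 15 per arm, the size is 3.2% for all levels, 4.0% for 2×2 and about 4.6% for Wilcoxon. At 30 and 45 per arm the 2×2 size is about 5.3-5.7%. The smaller expected count in the 2×2 table is 15 × (1 − 0.725) = 4.1 at 15 per arm, which is low, but the simulated error rates stay near nominal.

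**The case for a change.** The best argument for a change is that the Study Rationale grouping does not settle the matter. It belongs to a single-arm benchmark, is not tied to the between-arm test, and does not cover likelihood of recommending, for which the documents give no cut at all. A reader cannot tell which table was meant. In small arms the choice matters, and stating it would take a line or two and no new data. For a broad shift the gain from using order is large, about 17 points at 15 per arm (48 − 31).

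The ambiguity stands. The step from ambiguity to a wrong test does not. The power loss requires a reading that no passage states, and chi-squared statistics is a generic term that does not exclude a trend version. Preferring the ordered test requires an assumed broad shift, for which the documents offer no evidence over a difference centred on one cut. The size of the gain rests entirely on assumed levels, distributions and numbers. The worry about choosing the layout late is fair in general, but the SAP is written in the past tense. If the analysis has been run, naming a cut-point now would not make it prespecified, and an added ordered test would be post hoc and could not recover planned power.

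**Conclusion.** No change to the plan follows. What is missing is detail: response levels, cut-point and test version for two survey items. An analyst holding the survey form would have the levels, and the report's tables would show which comparison was made. On the two-by-two reading, which the Protocol's own grouping suggests, nothing is lost for that proportion. On the unordered all-levels reading, the loss against a broad shift would be about 16-17 points at 15 to 30 per arm under the assumed distributions, but an ordered test gives up 5 to 12 points elsewhere: 12 to the 2×2 test when the shift is concentrated at the grouping (35 − 23), and 5 and 11 to the all-levels test in the last two patterns (31 − 26 and 16 − 5), all at 15 per arm. That is a trade-off and not an error. No stated power is missed, because none is stated, and the 85% benchmark concerns one arm and is not decided by this test. All power figures assume a four-level scale, equal allocation and independent answers; they illustrate the ranking of the tests and do not estimate this trial's power.

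### The FSFI and FSDS-R change models name no baseline term; if arm is the only term, adjusting for baseline score would usually give a more precise between-arm estimate at almost no cost

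*SAP*

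**What the plan says.** The SAP (Statistical analysis) gives these two scales one sentence: "We constructed linear regression models to compare changes in FSFI and FSDS-R from baseline to 12 weeks for each group". It specifies linear regression with change as the outcome. It does not list the predictors, does not say whether baseline score is among them, and does not name the coefficient to be reported. The Protocol has no statistical section that fills this in.

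The sentence before it, on the primary outcomes, is explicit about the contrast: "We used chi squared statistics to examine differences in primary outcomes between groups". The SAP classes both scales as exploratory.

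Four points in the Protocol bear on the matter:

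- Women are randomised to two groups, and the comparator has a stated purpose: "The use of an active control allows the study to control for group support and attention" (Study Intervention or Experimental Manipulation Description).
- Groups are planned at roughly 12 to 15 women, with smaller ones allowed: "If participant number is fewer than 12 people per group, the sessions can still be held" (Strategies for Recruitment and Retention). Total sample size and number of groups per arm are not given.
- "At the 12 week mark, a final set of surveys will be sent out, identical to the baseline surveys", apart from a few listed topics (Administration).
- "If a participant misses more than 2 meetings, they are withdrawn from the study" (Discontinuation/Withdrawal). The same section ends survey follow-up for women who have left the study.

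**The concern.** A regression of change on arm alone subtracts the whole baseline score from the 12-week score, which fixes the baseline slope at 1. A model that also contains baseline score estimates that slope. It returns the same arm effect whether the outcome is the change or the 12-week score. When the true slope is below 1, as it is with equal SDs and a correlation below 1, the fixed slope over-corrects for chance baseline differences and adds noise to the arm comparison.

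At stake is the width of the confidence interval for mindfulness versus education on the SAP's only measures of sexual function and sexual distress. With groups of this size the intervals will be wide in any case, so avoidable width matters. A lesser matter is that the sentence ends on a per-group phrase where the one before it states a between-group contrast.

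**Working it through.** There is no figure in the plan to reproduce: the documents give no power calculation, SD, correlation or effect size for these scales. The check is therefore a comparison of two estimators over assumed values.

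**Inputs.** n per arm: 12, the lower end of the stated group size, with 8, 15 and 30 as a range. Smaller groups are allowed, withdrawals reduce the analysed number, and the Protocol allows for further rounds ("If there are further six-week sessions, a participant can move to a later session that may fit their schedule"). rho is the correlation of baseline with 12-week score, and k is the 12-week SD divided by the baseline SD; both are assumptions. Also assumed: equal arms, common rho and SDs in both arms, normal scores, complete data and independent women (no clustering by session group).

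**Formulas**, with baseline SD = 1 and N = 2n:

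- Change on arm alone: variance = (1 + k² − 2·rho·k)·(2/n)
- Baseline-adjusted: variance = k²·(1 − rho²)·(2/n)·[1 + 1/(N − 4)]
- Ratio (adjusted/change) = k²·(1 − rho²)·[1 + 1/(N − 4)] / (1 + k² − 2·rho·k)

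The bracket is the price of estimating the slope.

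**Equal SDs (k = 1).** The ratio reduces to [(1 + rho)/2]·[1 + 1/(N − 4)]. At 12 per arm, N − 4 = 20 and the bracket is 1.05:

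- rho 0.3: 0.65 × 1.05 = 0.68
- rho 0.5: 0.75 × 1.05 = 0.79
- rho 0.7: 0.85 × 1.05 = 0.89
- rho 0.9: 0.95 × 1.05 = 1.00

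Variance ratios at other sizes, with the 95% CI width ratio in brackets (this also counts the lost degree of freedom):

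| n per arm | rho 0.3 | rho 0.5 | rho 0.7 | rho 0.9 | break-even rho |
|---|---|---|---|---|---|
| 8 | 0.704 (0.845) | 0.812 (0.908) | 0.921 (0.967) | 1.029 (1.022) | 0.846 |
| 12 | 0.683 (0.828) | 0.788 (0.890) | 0.892 (0.947) | 0.997 (1.002) | 0.905 |
| 15 | 0.675 (0.823) | 0.779 (0.884) | 0.883 (0.941) | 0.987 (0.995) | 0.926 |
| 30 | 0.662 (0.814) | 0.763 (0.874) | 0.865 (0.930) | 0.967 (0.984) | 0.965 |

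As an absolute example at 12 per arm and rho 0.5, the half-width falls from 0.85 to 0.75 SD.

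**Unequal SDs**, 12 per arm, rho 0.5: the ratio is 0.60 (k = 0.8), 0.70 (0.9), 0.79 (1.0), 0.86 (1.1), 0.94 (1.25) and 1.01 (1.5). At 12 per arm the change score is as precise or better for rho from 0.77 to 0.97 (k = 1.1), 0.63 to 0.90 (k = 1.25) and 0.47 to 0.80 (k = 1.5).

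**Worst case.** Apart from the bracket, the ratio cannot exceed 1, because (1 + k² − 2·rho·k) − k²·(1 − rho²) = (1 − rho·k)² ≥ 0. The most that adjustment can lose is therefore 1/(N − 4) in variance: 1/12 = 8.3%, 1/20 = 5.0%, 1/26 = 3.8% and 1/56 = 1.8% at 8, 12, 15 and 30 per arm. For k above 1 this occurs at rho = 1/k, where the true slope is exactly 1.

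**Simulation**, 40,000 complete-data trials per setting, true difference 0.5 SD, 12 or 15 per arm, rho 0.3 to 0.9: mean estimates were 0.498 to 0.503 (change) and 0.498 to 0.502 (adjusted). At 12 per arm and rho 0.5 the variance ratio was 0.786, against 0.788 from the formula.

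**The case against.** The strongest reply is that the SAP never says arm was the only term. That stands: if baseline was in the model, the precision point disappears and only the request to list the terms remains. A reader might infer from the silence that baseline was left out; the documents do not show it.

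Second, the gain depends on the values assumed. This also stands. At 12 per arm with equal SDs, the interval is 11% narrower at rho 0.5 but only about 5% narrower at rho 0.7, and no narrower at rho 0.9. Entry on self-reported low desire could compress the baseline spread and push k above 1, where the gain is smallest; that is plausible but unproven. The half-widths in SD units also ignore clustering by session group.

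Third, a reader might take the closing phrase of the SAP sentence to mean separate within-arm analyses. The wording is loose, but that is the less natural reading. The verb is one of comparison, the design is randomised, and an active control has little purpose without a between-arm contrast.

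Fourth, the scales are exploratory and the SAP is in the past tense, so a newly adjusted model may be post hoc. That limits the weight of the point. It does not remove the case for stating the terms.

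**Conclusion.** The point holds as a modest, conditional one. The model is under-specified, and if arm is its only term, precision is probably being given away. At 12 per arm with equal SDs, adjustment cuts the variance by about 32%, 21% and 11% at rho 0.3, 0.5 and 0.7, and by essentially nothing at 0.9. It can cost at most 5% at that size, and the gain shrinks or vanishes when the 12-week SD exceeds the baseline SD. The correlation, SDs and arm sizes are assumptions.

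Two stronger conclusions are not supported. One is that a change-score regression is biased or invalid: under randomisation the choice between these models introduces no bias if 12-week data are complete or non-informatively missing. The other is the opposite, that randomisation guarantees an unbiased comparison. Women who miss more than two meetings are withdrawn and then receive no further surveys, so the women analysed at 12 weeks may be a group selected after randomisation. That is a separate problem affecting either model, and adjusting for baseline does not by itself settle it.

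The primary chi-squared analysis is untouched. This is a nearly free improvement to consider, and it does not correct an error.

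**What to change.** Rewrite the SAP sentence so that, for each scale, the 12-week score (or the change) is regressed on randomised arm and baseline score. Report the adjusted between-arm difference with its 95% CI, and replace the per-group ending with a between-group contrast, which is the likely intent. If baseline was already in the model, say so; nothing else changes. If results already exist without it, show the adjusted model beside the original and label it post hoc.

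The cost is one sentence and at most one term per model. Residual degrees of freedom go from N − 2 to N − 3, for example from 22 to 21 at 12 per arm. No new data are needed, because the change score already uses the baseline score.

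### FSFI and FSDS-R appear to be collected at the end of the sessions in both arms, but the SAP models only the change to 12 weeks and leaves the week-7 scores unused

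*SAP*

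**What the plan says.** The SAP (Statistical analysis) labels FSFI and FSDS-R exploratory, sets them at 12 weeks and gives one analysis: "We constructed linear regression models to compare changes in FSFI and FSDS-R from baseline to 12 weeks for each group". Its only 7-week analysis concerns the primary outcome, satisfaction and likelihood of recommending the group. It states no method for missing data.

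The protocol pays women for three assessments (Strategies for Recruitment and Retention). Under Administration, the second comes when the course ends: "Following the completion of the sessions, a survey will be sent to participant". Its content is given by subtraction from baseline: "These surveys will be identical to the baseline surveys, excluding the surveys on Demographics, Relationship Variables, Frequency of Sexual Activities, and Medical Variables". The third has the same reduced content: "At the 12 week mark, a final set of surveys will be sent out, identical to the baseline surveys", with the same four forms left out.

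Under Discontinuation/Withdrawal the protocol says: "Data up until the point a participant discontinued the study will be included in the study". The same section stops surveys once a woman discontinues, and withdraws women who miss more than two meetings.

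**The concern.** The intervention lasts six weeks, and 12 weeks falls about six weeks after it ends (12 - 6, counting from the first session). A benefit could peak at the end of the course and fade, or build with practice. A single late reading shows neither. These outcomes are exploratory, so their main use is to guide the next study, and the shape of the response over time is part of what that study needs to know.

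There is also a question of who enters the model. A woman with baseline and week-7 scores but no 12-week survey has post-treatment data on both scales, yet has no value for a baseline-to-12-week change. If returning the last survey is related to how she was doing at week 7, the 12-week comparison can be biased, and the score that would help to correct it goes unused.

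**Working it through.** The documents give no SD, correlation, attrition rate, effect size or total sample size for these scales, so there is no figure of the plan to reproduce. Steps 1 and 2 compare the texts. Steps 3 to 5 are illustrations on assumed inputs.

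**1. Are the week-7 scores collected?** The SAP analyses change from baseline, so both scales are in the baseline set. The end-of-session survey is the baseline set minus four named forms, and neither scale is among the four. No arm is exempted. Both scales are therefore due at the end of the sessions in both arms. This is an inference, because the protocol does not name either scale.

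**2. Who could contribute?**

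| Surveys returned | 12-week change model (default) | Two-visit model |
|---|---|---|
| Baseline, week 7, week 12 | yes | yes |
| Baseline, week 7 | no | yes |
| Baseline, week 12 | yes | yes |
| Baseline only (e.g. withdrawn during the sessions) | no | no |

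Only the second row changes.

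**3. Precision if loss is random.** Assume correlations of 0.6 (baseline with each follow-up) and 0.7 (week 7 with week 12), with both analyses adjusted for baseline.
- Partial correlation of the two follow-ups given baseline: r = (0.7 - 0.6 x 0.6)/(1 - 0.6 x 0.6) = 0.34/0.64 = 0.53, so r squared = 0.282.
- With a share m of 12-week scores missing, the ratio of standard errors is about sqrt(1 - 0.282m).
- m = 15%: sqrt(0.958) = 0.979, a fall of 2.1%. m = 25%: sqrt(0.929) = 0.964, a fall of 3.6%. m = 35%: sqrt(0.901) = 0.949, a fall of 5.1%.
- Simulation with 30 per arm (4000 replicates) gives 0.229 to 0.224, 0.247 to 0.237 and 0.260 to 0.248, falls of 2.2%, 4.0% and 4.6%.
- Wider range: for m of 10-30% and a correlation of 0.5-0.8 between the week-7 and week-12 changes, the effective sample size rises by 2.6% to 23.8%. At 15 per arm and m = 20%, 12.0 per arm becomes 12.6-13.8, and power for a 0.8 SD difference (two-sided 5%) goes from 0.50 to 0.52-0.56. At m = 0 nothing is recovered.

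**4. Bias if loss is not random.** Same correlations, true effect 0.60 SD at both visits, week 7 complete, loss more likely after a poor change. The ranges cover several runs that differ in the amount of loss and in how the dropout slope is scaled.

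| 12-week loss depends on | 12-week-only estimate | With week 7 |
|---|---|---|
| Week-7 change, intervention arm only | 0.63-0.74 | about 0.60 |
| Week-7 change, both arms | 0.56-0.59 | about 0.60 |
| 12-week change, both arms | 0.53-0.57 | 0.55-0.58 |

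The sign changes with the mechanism. The largest bias, 0.74 - 0.60 = 0.14 SD, is less than half the simulated standard error at 15 per arm (0.32-0.38).

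**5. Can week 7 show fading?** With complete data, the standard error of the week-7 minus week-12 difference in arm effects is sqrt(2 x 2(1 - 0.7)/n) = sqrt(1.2/n): 0.28 SD at 15 per arm and 0.20 at 30. Power is about Phi(difference/SE - 1.96). For a fade from 0.6 to 0.3 SD it is 18% at 15 per arm and 32% at 30. For complete disappearance of a 0.6 SD effect it is 56% and 85%.

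**The case against.** Twelve weeks is a legitimate time point, and the SAP names it in advance for outcomes it calls exploratory. The primary outcome is untouched and no confirmatory claim depends on these models. That stands. It limits the weight of the point and is why the 12-week contrast should be kept.

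A reader might infer that the SAP discards women without a 12-week survey, or breaks the protocol's rule on data before discontinuation. The documents do not support that. The SAP states neither exclusion nor imputation; dropping these women is what a change-score regression does by default. The protocol says such data are included in the study, not in every model, and a woman who stops after week 7 can still count in the 7-week primary outcome.

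A reader might also infer that the 12-week analysis overstates the effect. That holds only under one assumed mechanism; the same mechanism in both arms reverses the sign. No attrition figure is given, so the number of women affected is unknown. Week 7 was also taken as complete in the simulations, whereas women withdrawn during the sessions have neither follow-up score.

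What survives is that the schedule implies a second efficacy measurement and the SAP has no use for it. That holds even with no dropout.

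**Conclusion.** The point holds in a limited form and is worth acting on. The plan omits an end-of-treatment contrast for both scales although the data appear to be collected, and by default it leaves out women seen at week 7 but not at week 12. The gain from repair is an estimate the plan otherwise lacks, about 2-5% off the 12-week standard error under the assumptions of step 3, and protection against bias only where loss depends on the observed week-7 score. If loss depends on the unseen 12-week score, little is recovered.

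It would be tempting to say that the week-7 data would settle whether a null 12-week result means no effect or a faded one. At the 12-15 women per group in the protocol they would not (total enrolment is not given). They would describe the course over time, with wide intervals. Confidence that the scales are collected at week 7 is good but not complete, because it rests on the inference in step 1.

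**What to change.** - In the protocol's survey schedule, name FSFI and FSDS-R and the visits at which each is completed. If they are not meant to be collected at the end of the sessions, correct the description of that survey.
- In the SAP, for each scale, specify one repeated-measures model with the week-7 and week-12 scores as outcomes; arm, visit, arm-by-visit and baseline score as terms; and correlation within woman. Include every randomised woman with a baseline and at least one follow-up score.
- Keep the 12-week arm difference as the named exploratory estimate. Report the week-7 difference with its confidence interval as descriptive.
- State the missing-at-random assumption, add a sensitivity analysis for it, and report how many women have each pattern of surveys, including those withdrawn during the sessions.

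The cost is SAP wording, a little analysis and one more exploratory contrast per scale; no new visits, women or data are needed. The SAP is written in the past tense, which suggests but does not prove that the 12-week analysis has been run. If it has, label the new model post hoc and show it beside the stated analysis, not in its place.
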